5.3 Study Effectiveness Assessments

5.3.1 Blinded Evaluators and Investigator's Global Assessment of Improvement

Blinded improvement assessments will be performed 12 weeks post the [REDACTED] or final laser treatment. Blinded Evaluators will be asked to assess the subject's before (baseline) and after photographs in one and/or both of the below methods:

- Determine the temporal order (before and after) of each photograph pair.

- Rate the degree of improvement observed from baseline using the Acne Scar Assessment Scale (ASAS)

A. Acne Scar Assessment Scale (ASAS): The ASAS is a static assessment scale that allows the Investigator to measure his/her impression of acne scar severity within the treatment area. The treatment area on each side of the face will be assessed separately, then will be averaged to obtain a global score.

Term	Grade	Description
Clear	1	No depressions are seen in the treatment area. Macular discoloration may be seen.
Very Mild	2	A single depression is easily noticeable with direct lighting (deep). Most or all of the depressions seen are only readily apparent with tangential lighting (shallow).
Mild	3	A few to several, but less than half of all the depressions are easily noticeable with direct lighting (deep). Most of the depressions seen are only readily apparent with tangential lighting (shallow).
Moderate	4	More than half of the depressions are apparent with direct lighting (deep).
Severe	5	All or almost all the lesions can be seen with direct lighting (deep).

□

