5.3.2 Investigator Assessments

[figure not shown]
At baseline, [REDACTED], the Investigator will assess the efficacy of the Cutera enlighten laser with the MLA handpiece attachment treatment using the ASAS, GAIS, and Skin Quality Rating Scale. Baseline photos of subjects may be used while assessing the ASAS, GAIS, and Skin Quality Rating Scale.

A. Acne Scar Assessment Scale (ASAS): The ASAS is a static assessment scale that allows the Investigator to measure his/her impression of acne scar severity within the treatment area. The treatment area on each side of the face will be assessed separately, then will be averaged to obtain a global score.

Term	Grade	Description
Clear	1	No depressions are seen in the treatment area. Macular discoloration may be seen.
Very Mild	2	A single depression is easily noticeable with direct lighting (deep). Most or all of the depressions seen are only readily apparent with tangential lighting (shallow).
Mild	3	A few to several, but less than half of all the depressions are easily noticeable with direct lighting (deep). Most of the depressions seen are only readily apparent with tangential lighting (shallow).
Moderate	4	More than half of the depressions are apparent with direct lighting (deep).
Severe	5	All or almost all the lesions can be seen with direct lighting (deep).

□

[REDACTED]	[REDACTED]

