7.4 Phone and Follow-Up Visits

There are [REDACTED] follow-up visits at [REDACTED] and 12 weeks [REDACTED] () following the final laser treatment.

The following procedures will be performed during the phone and follow-up visits:

1. Assessment of Concomitant Medications: Assess and record any additions, changes and/or deletions in prescription and nonprescription concomitant medications since the previous study visit.
2. Assess for any ongoing, previously reported, and/or new adverse events and expected adverse device effects.

During the follow-up visits:

1. Cleanse subject's treated area with a mild cleanser to remove any cosmetics, lotions, or perfumes.
2. Photographs of the treated area(s) will be taken at the same pre-defined angles (Section 5.5).
3. Investigator will assesses the efficacy of the Cutera enlighten laser with the Micro-Lens Array handpiece attachment treatment using the ASAS, [REDACTED]

8. ADVERSE EVENTS and ADVERSE DEVICE EFFECTS

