11.3.2 Primary Efficacy Analysis

The primary endpoint is a responder, where a clinical response is defined as at least two of the three blinded reviewers selecting the correct order of treatment with at least a one-point improvement in the ASAS from baseline to 12 weeks. The primary hypothesis is as follows:

$H_0: \Pi = 0.5$

vs.

$H_A: \Pi \neq 0.5$,

where Π is the population response rate. The primary analysis will place an exact two-sided 95% confidence interval around the observed response rate and compare the lower bound to 50%. If the lower bound exceeds 50% the primary hypothesis will be rejected in favor of the response rate being greater than 50%.

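### Section 5.3.1 asks blinded evaluators to rate improvement from baseline on a static severity scale, so if their ASAS is the one used in 11.3.2 it may add little evidence beyond the photo-order call

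*Combined protocol and SAP*

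**What the plan says.** Section 5.3.1 has blinded evaluators assess the baseline and 12-week "photographs in one and/or both of the below methods". The first method is to "Determine the temporal order (before and after) of each photograph pair". The second is to "Rate the degree of improvement observed from baseline using the Acne Scar Assessment Scale (ASAS".

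Directly below, the scale is described: "The ASAS is a static assessment scale that allows the Investigator to measure his/her impression of acne scar severity within the treatment area". It has five grades, from 1 (clear) to 5 (severe), each describing one scar state. Each side of the face is graded and the two grades are averaged.

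Section 11.3.2 defines a responder as a subject for whom at least two of three blinded readers choose the correct order, "with at least a one-point improvement in the ASAS from baseline to 12 weeks". It does not name the ASAS rater; neither does 5.1.1.

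The treating side also produces ASAS scores. Section 5.3.2 has the investigator rate the scale and adds: "Baseline photos of subjects may be used while assessing the ASAS, GAIS, and Skin Quality Rating Scale". Section 7.4 repeats the investigator rating at follow-up visits: "Investigator will assesses the efficacy of the Cutera enlighten laser with the Micro-Lens Array handpiece attachment treatment using the ASAS".

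**The concern.** None of the five ASAS grades expresses improvement. To rate improvement directly from a photograph pair, an evaluator needs a view on which image came first. That view is either supplied, so the rating is not masked to time, or it is the evaluator's own answer to the ordering task. In the second case, someone who has called the better-looking image the later one has already settled the direction of the ASAS change. The visible text does not require photographs to be graded singly, the visit to be masked for grading, the order calls to be locked first, or the change to be computed afterwards.

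This matters because the study is open-label and single-arm, so masked reading is its main protection against expectation of benefit. The one-point condition is there to show that a detectable difference is a full grade of scar improvement. If it follows the order call, a subject can count as a responder because the photographs are distinguishable for some other reason.

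**Working it through.** **Inputs from the documents.** Null rate 0.50, assumed response rate 0.75, 40 evaluable subjects and stated power of 80% (11.1 and 11.3.2). Success means that the lower bound of an exact two-sided 95% interval exceeds 50% (11.3.2). The order half needs two of three readers correct.

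**Assumptions, not in the documents.** Per-reader ordering accuracy *c*, with readers independent; and *k*, the share of correctly ordered subjects who also show the one-point ASAS gain.

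**1. The plan's own test.** Find the smallest count *r* with P(X ≥ *r* | 40, 0.50) ≤ 0.025.
- *r* = 26 gives 0.0403, which is too large. *r* = 27 gives 0.0192. Success therefore needs 27 of 40.
- Power at 0.75 is P(X ≥ 27 | 40, 0.75) = 0.897, so the stated 80% is not reproduced. The difference is conservative and does not bear on this point.

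**2. Order half.** P(at least 2 of 3 correct) = *m* = *c*³ + 3*c*²(1 − *c*).
- *c* = 0.50: 0.125 + 0.375 = 0.500
- *c* = 0.60: 0.216 + 0.432 = 0.648
- *c* = 0.65: 0.275 + 0.444 = 0.718 (from unrounded terms)
- *c* = 0.70: 0.343 + 0.441 = 0.784

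**3. Pure guessing.** The composite rate is *m* × *k* = 0.50 × *k*, which is at most 0.50. However tightly the halves are linked, the chance of study success is at most 0.0192.

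**4. Order detectable from cues other than scars, with no true scar improvement.** The chance of study success is P(X ≥ 27 | 40, *m* × *k*):

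| *c* | *m* | *k* = 0.3 | *k* = 0.5 | *k* = 0.7 | *k* = 1 |
|---|---|---|---|---|---|
| 0.60 | 0.648 | <0.000001 | 0.00001 | 0.004 | 0.43 |
| 0.65 | 0.718 | <0.000001 | 0.00005 | 0.021 | 0.79 |
| 0.70 | 0.784 | <0.000001 | 0.0003 | 0.073 | 0.96 |

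The last column is full coupling: the ASAS half simply repeats the order call. Under masked grading *k* is the rate of one-point drops by error, assumed to be 10–30%. The composite rate then runs from 0.648 × 0.10 = 0.065 to 0.784 × 0.30 = 0.235, and the chance of success is below 0.000001 throughout.

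**5. How much coupling is needed.** The composite rate exceeds 0.50 only if *k* > 0.50/*m*: 0.50/0.648 = 0.77, 0.50/0.718 = 0.70 and 0.50/0.784 = 0.64.

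**The case against.** The strongest reply is that 5.3.1 can be read harmlessly: grade each photograph set, average the two sides, and subtract. Calling the scale static and deriving a global score both suit that reading, and 11.3.2 may use improvement as shorthand for the difference. This stands in part. The wording allows masked grading but does not require it. A reader might infer that the scale itself forces order-aware rating, or that evaluators are told which image is baseline. The documents support neither.

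The link to the primary endpoint is conditional. No section names the ASAS rater for 11.3.2, evaluators may do only one of the two methods, and the scale is described as the investigator's measure. If the investigator's score is meant, this mechanism does not reach the primary endpoint. The issue would then be an unmasked rating for which baseline photographs may be consulted. This stands in full.

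Dependence between the halves is not an error. They should correlate if treatment works, and the plan tests one composite rate without assuming independence. This also stands.

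Full coupling is an extreme. An order call can fix only the direction of change, while the criterion is a full point on a two-side average, so side-level drops must total at least two grades. Section 5.5 also standardises lighting, positioning, camera settings and make-up removal, which limits photographic cues. Both points reduce the likely size. Neither addresses residual changes in the skin itself, such as redness or pigment.

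Finally, much of Section 7 and the appendices is blacked out, so a reading procedure may exist there. The point is confined to the visible text.

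**Conclusion.** The point holds as a conditional weakness. The instruction in 5.3.1 does not fit the scale it uses, and the visible text does not keep the order judgement out of the ASAS rating. If the evaluators' ASAS is the one in 11.3.2, the one-point condition may add little separate evidence.

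A reader might infer that coupling produces false positives by raising the null composite rate from about 10% (0.50 × an assumed 0.20) towards 50%. It does not: 50% is the rate the hypothesis tests against, and the error there is 0.0192. Harm requires both that order be recognisable from something other than scars and that coupling be strong. Under assumed accuracies of 0.60, 0.65 and 0.70, the limiting chance of success without scar improvement is about 0.43, 0.79 and 0.96. It falls to 0.004, 0.021 and 0.073 if 70% of correctly ordered subjects also show the one-point gain. The documents give neither the accuracies nor the degree of coupling, so these figures show how much protection could be lost, not what is expected.

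**What to change.** Replace the second method in 5.3.1 with:

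*Each evaluator assigns a static ASAS grade (each side, then averaged) to each photograph set singly, in random sequence across subjects and visits, with visit and date masked, before and separately from the paired-photograph ordering task. The statistician computes the change from baseline.*

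Require both methods, so that a blinded ASAS always exists. State in 11.3.2 that this computed blinded change is the ASAS component of the responder definition, and give the rule for combining three readers, such as the median. Reconcile 5.3.1, 5.3.2, 7.4 and 11.3.2 on whose ASAS counts for which endpoint.

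The cost is a few sentences and a second short reading session with the same readers and photographs. Single-image grades will be somewhat noisier than side-by-side ratings.

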5.3.2 Investigator Assessments

[figure not shown]
At baseline, [REDACTED], the Investigator will assess the efficacy of the Cutera enlighten laser with the MLA handpiece attachment treatment using the ASAS, GAIS, and Skin Quality Rating Scale. Baseline photos of subjects may be used while assessing the ASAS, GAIS, and Skin Quality Rating Scale.

A. Acne Scar Assessment Scale (ASAS): The ASAS is a static assessment scale that allows the Investigator to measure his/her impression of acne scar severity within the treatment area. The treatment area on each side of the face will be assessed separately, then will be averaged to obtain a global score.

Term	Grade	Description
Clear	1	No depressions are seen in the treatment area. Macular discoloration may be seen.
Very Mild	2	A single depression is easily noticeable with direct lighting (deep). Most or all of the depressions seen are only readily apparent with tangential lighting (shallow).
Mild	3	A few to several, but less than half of all the depressions are easily noticeable with direct lighting (deep). Most of the depressions seen are only readily apparent with tangential lighting (shallow).
Moderate	4	More than half of the depressions are apparent with direct lighting (deep).
Severe	5	All or almost all the lesions can be seen with direct lighting (deep).

□

[REDACTED]	[REDACTED]

5.3.3 Subject Satisfaction Assessment

5.4 Study Safety Assessments

5.4.1 Incidence and Severity of Adverse Events:

Following the first laser treatment, adverse effects (AEs) will be assessed post-treatment and at each subsequent visit using the following scale:

- 1= mild: requires minimal or no treatment and does not interfere with the subject's daily activities.
- 2= moderate: may cause some interference with functioning.
- 3= severe: interrupts subject's usual daily activity and may require treatment.

5.4.2 Treatment-related Discomfort

After each laser treatment, subjects will be asked to rate the average amount of discomfort experienced during treatment and immediately after laser treatment using the Pain Rating Scale (VAS Scale) Appendix 2.

5.4.3 Phone Follow-up

5.5 Photographs

Standardized digital photographs will be taken of each subject's treatment area at baseline, prior to and post all laser treatments and at each follow-up visit. Treatment area will be cleansed and any jewelry and make-up will be removed from the area being photographed. For facial photographs, hair will be pulled away from the face with a headband.

Facial photographs will be obtained from at least 3 angles: with the subject facing forward, 45° to the right and 45° to the left. Photographs will be taken in the same windowless room equipped with adequate lighting. The room lighting, camera positioning and subject positioning should be consistent for all study visit photographs. Digital camera settings should remain the same for all photographs and the highest resolution settings should be utilized.

5.6 Study Discontinuation

Cutera, Inc. (the sponsor) has the right to terminate this study at any time. Reasons for terminating the study may include, but are not limited to, the following: incidence or severity of adverse events in this or other studies indicates a potential health hazard to subjects; subject enrollment is unsatisfactory; number of protocol deviations is unacceptable; data recording is inaccurate or incomplete; or questionable study site compliance with ICH-E6, Good Clinical Practice²³.

5.7 Investigator Selection

The Investigator(s) will be invited to participate in the study based on his or her medical specialty, experience conducting clinical research studies and experience in the use of light-based devices for aesthetic indications. Access to potential study subjects and the Investigator's sincere interest in this study along with expressed willingness to cooperate with the study process and requirements was also considered.

6. STUDY POPULATION

6.1 Study Subject Recruitment and Selection

Approximately 45 male or female subjects, ages 18 to 65, with Fitzpatrick Skin Type I-VI who desire laser treatment for moderate to severe facial acne scars. Subjects will be recruited to participate from the local population. Subjects may also be recruited from the Investigator's existing patient database or from patients who present themselves to the study site requesting treatment. Only subjects who meet all eligibility criteria and who provide written informed consent will be enrolled into the study.

Each subject will be evaluated by the Investigator to assess his/her suitability for entry into the study according to the following inclusion and exclusion criteria.

6.1.1 Inclusion Criteria

To be included in the study, subjects must meet all of the following Inclusion Criteria:

1.	Subject must be able to read, understand and sign the Informed Consent Form.
2.	Female or Male, 18 to 65 years of age (inclusive).
3.	Fitzpatrick Skin Type I – VI (Appendix 6).
4.	Subject desires treatment for acne scars and wishes to undergo laser treatments for improvement.
5.	Subject has bilateral moderate to severe signs of facial acne scarring.
6.	Must be willing to have Cutera enlighten laser with the Micro-Lens Array handpiece attachment treatments and able to adhere to the treatments, follow-up visit schedule, and post-treatment care instructions.
7.	Willing to have very limited sun exposure and use sunscreen on the treatment area every day for the duration of the study, including the follow-up period.
8.	Willing to have digital photographs taken of the treatment area and agree to use of photographs for presentation (educational and/or marketing), publications, and any additional marketing purposes.
9.	Agree to not undergo any other procedure(s) or treatment(s) for acne scars during the study and has no intention of having such procedures performed during the course of the study.
10.	For female subjects: not pregnant or lactating and is either post-menopausal, surgically sterilized, or using a medically acceptable form of birth control at least 3 months prior to enrollment and during the entire course of the study.,

6.1.2 Exclusion Criteria

Subjects will be excluded from the study if they meet any of the following Exclusion Criteria:

1.	Participation in a clinical trial of another drug, or device administered to the treatment area, within 6 months prior to enrollment or during the study.
2.	Any type of prior cosmetic treatment to the target area within 6 months of study participation, such as laser procedures, facial fillers, i.e. (Bellafill) and those used for general aesthetic correction, facial peel, lightening creams, or facial surgery.
3.	Use of prescription topicals in the treatment area within one month prior to treatment or use of topical agents one week prior to treatment that may cause facial sensitivity.
4.	Suffering from significant skin conditions in the treated areas or inflammatory skin conditions, including but not limited to, open lacerations or abrasions, hidradenitis, rash, infection, or dermatitis of the treatment area prior to treatment (duration of resolution as per the Investigator's discretion).
5.	Pregnant and/or breastfeeding, or planning to become pregnant.

6.	Significant concurrent illness, such as diabetes mellitus, immunosuppression/immune deficiency disorders (including HIV infection or AIDS) or using immunosuppressive medication.
7.	Hypersensitivity to light exposure.
8.	Any use of medication that is known to increase sensitivity to light according to the Investigator's discretion.
9.	History of keloid scarring, hypertrophic scarring or abnormal wound healing or prone to bruising.
10.	Has a history of squamous cell carcinoma or melanoma in the treatment area.
11.	History of epidermal or dermal disorders (particularly if involving collagen or microvascularity), including collagen vascular disease or vasculitic disorders.
12.	A history or active skin condition that in the opinion of the Investigator may interfere/confound with the treatment.
13.	History of connective tissue disease, such as systemic lupus erythematosus or scleroderma.
14.	History of disease stimulated by heat, such as recurrent herpes simplex and/or herpes zoster (shingles) in the treatment area, unless treatment is conducted following a prophylactic regimen.
15.	History of pigmentary disorders, particularly tendency for hyper- or hypopigmentation, or any that are considered not acceptable by the study investigator.
16.	Has used oral isotretinoin (Accutane or therapeutic vitamin A supplements of \geq 10,000 units per day) within 12 months of initial treatment or plans on using during the course of the study (note: skin must regain its normal degree of moisture prior to treatment, e.g. lack of noticeable skin flaking and peeling).
17.	Excessively tanned or active sun tan in facial area to be treated, or unable/unlikely to refrain from tanning during the study.
19.	Excessive facial hair in the area to be treated (beards, sideburns, and/or moustache,) that would interfere with diagnosis, assessment, and treatment.
20.	As per the Investigator's discretion, any physical or mental condition which might make it unsafe for the subject to participate in this study, including excessive alcohol or drug abuses, or a condition that would compromise the subject's ability to comply with the study requirements.

6.2 Subject Numbering

If a subject completes the Informed Consent Form, meets the study eligibility criteria and is willing to participate, the subject will be assigned a study subject identification number. This number is comprised of a site number (which is provided by the sponsor) and a sequential subject number and the subject initials (first and last names).

6.3 Subject Discontinuation Criteria

[figure not shown]
If possible, every subject should remain in the study until completion of the required follow-up period. However, participation in this study is completely voluntary and a subject can choose to withdraw from the study at any time. Decision to withdraw will not affect or prejudice the subject's continued medical care in any way. In those instances, the investigator will attempt to obtain a final clinical assessment and an adverse device effect evaluation for the subject prior to this withdrawal. A subject will be considered

lost to follow-up only after three unsuccessful, documented attempts to contact the subject have been made.

In addition, a subject can be discontinued for any of the following reasons: the Principal Investigator decides that continuing in the study would not be in the subject's best interest, a subject is noncompliant with the protocol, a subject has a serious reaction to the treatment, a subject develops any of the exclusion criteria during the study period or the study is stopped by the study sponsor.

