8.2 Recording AEs, ADEs and SADEs

All AEs/SAEs or ADEs/SADEs will be: (1) evaluated and must be recorded in the subject's medical chart and in the study case report forms (CRFs); (2) monitored and tracked from the time of the first treatment with the Cutera Enlighten laser system.

At each contact with the subject, the investigator must seek information on AEs/ADEs/SADEs by specific questioning and, as appropriate, by examination. AEs/ADEs/SADEs may be observed by the investigator and/or clinical research staff, elicited from the subject and/or family member or volunteered by the subject. All observed and volunteered adverse signs and symptoms, anticipated or unanticipated, regardless of severity or frequency, will be recorded in the case histories (medical chart and CRFs). Included in the description should be the nature of the sign or symptom, the date of onset, date of resolution (duration), the severity, anticipated or unanticipated, the relationship to study treatment or other therapy, the action taken (if any), and the outcome.

All SAEs/SADEs, anticipated or unanticipated, must be reported to Cutera immediately but not later than 5 working days. The SADE must be recorded in: (1) the AE CRF and (2) a written report must be submitted to Cutera within five (5) working days after the investigator first learns of the event and is to include a full description of the event and sequelae, in the format detailed by the Cutera Serious Adverse Event Form.

8.3 Follow-up of subjects after AEs/ADEs and SAEs/SADEs:

All reported AEs/ADEs/SAEs/SADEs should be followed until resolution or until the subject's participation in the study ends. Resolutions of AEs/ADEs/SAEs/SADEs are to be documented on the appropriate CRFs. All ADEs that result in permanent discontinuation from this clinical trial, whether serious or not, should also be reported on the subject Non-Completion of Study Form.

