11.3.1 Analysis Sets

The efficacy analysis set will include all subjects who received one facial laser treatment session and complete at least one follow-up visit. The safety analysis set will include all subjects enrolled in the study who had at least one laser treatment session.

Missing data will not be imputed for efficacy or safety endpoints.

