11.3.4 Safety Analyses

Safety variables will be analyzed descriptively. The safety variables for this study are:

- Incidence and severity of adverse effects during study duration (to be displayed descriptively as counts and frequency distributions)

Enrolled subjects who received at least one treatment will be included in the safety analyses. Device-related and procedure-related adverse effects (AEs) and subjects who prematurely terminate from the study due to an adverse device effect, including the treatment-related pain ratings, as reported on case report forms will be tabulated and analyzed. For a given AE term, counting will be done by subject, not by event, i.e. for a subject reporting the same AE more than once, the event will be counted only once, at the most severe and most-related occurrence. The number and percentage of subjects experiencing each AE Term will be descriptively summarized. Statistical hypothesis testing will not be performed for safety data.

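### On the legible text, Section 6.3 lets a serious reaction end a subject's study participation, and Section 8.3 then lets adverse-event follow-up end with it

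*Combined protocol and SAP*

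**What the plan says.** Section 6.3 opens with an aim: "If possible, every subject should remain in the study until completion of the required follow-up period". It then says that participation is voluntary and a subject may withdraw at any time, and continues: "In those instances, the investigator will attempt to obtain a final clinical assessment and an adverse device effect evaluation for the subject". A separate paragraph lists further grounds on which a subject can be discontinued. Among them: "a subject has a serious reaction to the treatment, a subject develops any of the exclusion criteria during the study period". That list is permissive, and it does not say whether what stops is the laser treatment or study participation.

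Two other sections show how the term is used. Section 8.3 refers to "All ADEs that result in permanent discontinuation from this clinical trial, whether serious or not", to be recorded on a non-completion form. Section 11.3.4 tabulates "subjects who prematurely terminate from the study due to an adverse device effect". Both describe an exit from the study.

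Section 8.3 also sets the end of safety follow-up: "All reported AEs/ADEs/SAEs/SADEs should be followed until resolution or until the subject's participation in the study ends". For efficacy, Section 11.3.1 states: "The efficacy analysis set will include all subjects who received one facial laser treatment session and complete at least one follow-up visit", and "Missing data will not be imputed for efficacy or safety endpoints".

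**The concern.** A subject who has a serious reaction to the device is the one whose later course matters most for the safety objective. As written, an investigator can discontinue that subject while the reaction is unresolved. Participation then ends, the duty to follow the event ends with it, and the sentence about a closing assessment does not clearly apply. Section 8.2 asks for the date of resolution, the duration and the outcome of every event, but the plan would not oblige anyone to obtain them.

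There is a second, lesser consequence. The 12-week outcome of such a subject may be missing. If the subjects removed would have responded less often than the rest, the single-arm response rate is pushed upward.

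**Working it through.** **1. The plan's own figures.** Section 11.1 states 80% power with 40 subjects at a 75% response rate against 50%, and 45 treated after 10% dropout. The inflation reproduces: 40 / 0.9 = 44.4, rounded up to 45. The power does not. With the exact two-sided 95% interval of Section 11.3.2, success needs 27/40 (lower bound 0.5087), and P(X ≥ 27 | 40, 0.75) = 89.7%. The stated figure is conservative and has no bearing on this point.

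**2. The rules side by side (legible text).**

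| | Subject withdraws | Investigator discontinues for a serious reaction |
|---|---|---|
| Closing assessment (6.3) | Attempted | Not stated |
| Follow-up of an unresolved event (8.3) | Ends with participation | Ends with participation |
| Counted in safety tables (11.3.4) | Yes, if treated | Yes, including as a termination due to a device effect |
| 12-week result (11.3.1) | Not imputed if missing | Not imputed if missing |

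The number of removals is therefore visible. What can be lost is how long the reaction lasted and whether it resolved. No legible rule keeps a subject on study but off laser treatment. The design would allow it: Section 5 gives subjects up to a set number of sessions, and Section 5.3.1 times the blinded assessment 12 weeks after the final one.

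The safety loss has no computable size, because the documents give no rate of serious reactions or of removals.

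**3. Size of the secondary efficacy effect.** Inputs from the plan: N = 45, null rate 0.50, planned rate 0.75, success if the exact lower bound exceeds 0.50. Assumptions, not in the documents: each subject is removed with probability r = 0.02 (0.02 × 45 = 0.9, about one subject) or r = 0.05; a fraction q of those removed would have responded; and everyone removed leaves the denominator.

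- Lower bound for x of n: the 0.025 quantile of Beta(x, n − x + 1). Minimum successes: 30/45 (0.5105), 29/44 (0.5008), 29/43, 28/42 (0.5045). 29/45 fails (0.4878).
- Response rate among those retained: p' = (p − rq) / (1 − r).
- Chance of success: the sum over m of P(M = m) × P(X ≥ c(m) | m, p'), with M ~ Binomial(45, 1 − r) and c(m) the minimum count for m.

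False success at p = 0.50 (nominal upper tail 2.5%):

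| r | q = 0 | q = 0.25 | q = 0.50 (no bias) |
|---|---|---|---|
| 0 | 1.8% | 1.8% | 1.8% |
| 0.02 | 2.8% | 2.4% | 2.0% |
| 0.05 | 4.2% | 2.9% | 1.9% |

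The q = 0.50 column shows the effect of the smaller n alone. Against it, selective removal adds at most 2.76 − 2.01 = 0.75 points (r = 0.02) or 4.18 − 1.91 = 2.27 points (r = 0.05). False success exceeds 2.5% only if q is below about 0.16 or 0.34 respectively.

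The largest shift in the expected rate occurs at q = 0:
- p = 0.50: 0.50/0.98 = 0.5102 and 0.50/0.95 = 0.5263, or 1.0 and 2.6 points.
- p = 0.75: 0.75/0.98 = 0.7653 and 0.75/0.95 = 0.7895, or 1.5 and 3.9 points.

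At the planned 75% the decision rarely turns on this. With all 45 assessed, power is 92.5%. The only failing count that one removal can turn into success is 29, because 29/44 passes; P(X = 29 | 45, 0.75) = 3.6%.

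**The case against.** **The missing sentence may be under the redactions.** The treatment-visit procedures (7.2), the adverse-event definitions (8.1), the risk section (9) and parts of the design section are blacked out, and the schedule in Appendix 1 cannot be read. A session-stopping rule may sit there, so a reader should not infer that the full protocol has none. What stands is narrower: the visible wording of 6.3 and 8.3 produces the gap and would need aligning with any such rule.

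**The plan already allows early stopping and favours retention.** Discontinuation is permissive, the opening aim is to keep everyone, and assessment is timed from the last session. All true. It would be wrong to read 6.3 as requiring removal after a serious reaction. But the aim carries no instruction for this case, and the same section names the reaction as a ground for discontinuation.

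**Section 8.2 protects the safety record.** Serious device effects must reach the sponsor within five working days in a written report that covers sequelae, and event records call for resolution and outcome. This narrows the loss. It does not close it, since a report at five working days cannot describe a course that is still unfolding.

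**The efficacy numbers rest on invented rates and on Section 11.3.1.** Agreed. That section does not say how to count a subject who has an earlier follow-up visit but no week 12; if such a subject stays in the denominator as a non-responder, the upward bias does not arise. A reader might go further and take all 45 − 40 = 5 allowed dropouts as reaction-related non-responders. Then p' = 22.5/40 = 0.5625 and false success is P(X ≥ 27 | 40, 0.5625) = 10.0%. Nothing in the documents supports that. Section 2 reports no severe side effects with a related 755 nm device, and ASAS grade 1 tolerates macular discoloration, so pigment change alone need not prevent a response.

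**Keeping everyone who newly meets an exclusion criterion could confound efficacy.** This is right. Isotretinoin use (criterion 16) and entry into another device trial (criterion 1) are examples in which week-12 scoring could mislead, so the fix must be narrower for this group.

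**Conclusion.** The point holds as a cheap improvement. On the legible text, a treated subject can be discontinued for a serious reaction with no distinction between ending laser sessions and ending participation. No closing assessment is specified for that route, and event follow-up stops when participation does. The resolution of a serious device reaction can go undocumented despite the safety objective, with Section 8.2 a partial safeguard.

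The main harm cannot be quantified from the documents. The efficacy effect is secondary: under assumed removal of 2% or 5%, false success at a true 50% lies between 1.9% and 4.2%, against 1.8% with everyone assessed, and the upper end requires that none of those removed would have responded. It is probably small. The documents do not support reading this as a hidden count of removals, a mandatory removal rule or a material threat to the primary conclusion.

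**What to change.** Amend Section 6.3 in four respects:

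1. A serious reaction may stop further laser sessions, but is not in itself a reason to leave the study. Whether treatment continues remains the investigator's decision.
2. Treated subjects who have not withdrawn consent are asked to attend the scheduled follow-up visits, including week 12 counted from the last session received.
3. The closing clinical assessment and device-effect evaluation apply to investigator-led discontinuations as well as voluntary withdrawals.
4. For an exclusion criterion newly met during the study, require safety follow-up and that closing assessment only. Efficacy scoring after confounding exposures stays outside this change.

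How to count subjects who still miss week 12 belongs in Section 11.3.1 and is a separate matter.

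The cost is a wording change. No new visit type is needed, because assessment is already timed from the final treatment. Subjects who stop early are asked for a few visits that they might otherwise skip, and the observed response rate may be slightly lower.
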